### **6.2.2. De Novo Subjects**

De Novo Subjects will be excluded from participation in this trial if they meet any of the following criteria:

1. Have any finding that in the view of the Investigator or the Medical Monitor would compromise the safety of the subject or affect their ability to adhere to the protocol visit schedule or fulfill visit requirements or make the subject unsuitable for participation in the study (including overall clinical assessment).
2. Diagnosis of primary progressive, secondary progressive, or progressive relapsing MS as defined by Lublin and Reingold [\[Lublin and Reingold 1996\]](#).
3. History of clinically significant cardiovascular, pulmonary, GI (e.g., inflammatory bowel disease, peptic ulcer disease), dermatologic, psychiatric, neurologic (other than MS), endocrine, renal and/or other major disease that would preclude participation in a clinical trial.
4. History of clinically significant recurring or active GI symptoms (e.g., nausea, diarrhea, dyspepsia, constipation) within 3 months of screening, including symptoms that require the initiation of symptomatic medical treatment (e.g., initiation of a medication to treat gastroesophageal reflux disease) or a change in symptomatic medical treatment (e.g., an increase in dose) within 3 months of screening.
5. History of malignancy, unless an exception is granted by the Medical Monitor (e.g., subjects with basal cell carcinoma that has been completely excised prior to study entry remain eligible).

CONFIDENTIAL

The information contained herein may not be used, disclosed, or published without the written consent of  
Biogen MA Inc.

6. Has a clinically significant medical condition or observed abnormality at screening (e.g., clinically significant physical examination finding, vital sign result, ECG result, or laboratory test result).
7. History of a myocardial infarction, including a silent myocardial infarction identified on ECG, or unstable angina.
8. History of clinically significant drug or alcohol abuse within the past year (per Investigator judgment).
9. Has a positive serology test for hepatitis B surface antigen, hepatitis C antibody, or human immunodeficiency virus (HIV) antibody at screening.
10. Has any of the following abnormal blood tests at screening:
  - Alanine aminotransferase (ALT) or aspartate aminotransferase (AST)  $\geq$  2 times the upper limit of normal (ULN)
  - Thyroid-stimulating hormone (TSH) level  $>10\%$  of the ULN at screening

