3.2. Demographics and Baseline Characteristics

For De Novo Subjects and Rollover Subjects who were in DMF treatment group in ALK8700 A302, demographics and baseline characteristics data will be collected at Visit 2. For Rollover Subjects who were in ALKS 8700 treatment group, these data will be carried over from information recorded in the antecedent ALK8700-A302 study unless otherwise specified.

Demographic data, including age, age category (18-19, 20-29, 30-39, 40-49, 50-55, and ≥ 55), as well as < 40 , ≥ 40), gender, race, weight, body mass index (BMI), ethnicity and region (US, non-US) will be summarized by enrollment group and overall.

Baseline disease characteristics will also be summarized by enrollment group and overall, using descriptive statistics. These include years since disease (MS) onset, years since diagnosis, number of relapses in the past 12 months, prior Disease modifying therapy, baseline Expanded Disability Status Scale (EDSS) scores and EDSS score category (0, 1-1.5, 2-2.5, 3-3.5, 4-4.5, and ≥ 5).

Medical history will be summarized by enrollment group and overall for the Safety Population. Demographic, baseline characteristics and medical history listings will be provided for all subjects.

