3.6.5. Clinical Laboratory Parameters

Laboratory parameters will be presented in conventional units. Only scheduled laboratory parameters will be included in the summaries. All laboratory data, including those collected at unscheduled visits, will be included in the listings. Laboratory results (baseline and change from baseline) for chemistry and hematology parameters for each visit during the entire study will be summarized. Percent change of lymphocyte count for each visit will be summarized.

For urinalysis, the number and percentage of subjects with abnormalities at any post-baseline visit will be summarized. In addition, the number and percentage of subjects with values considered potentially clinically significant (PCS) occurring at any post-baseline visit for selected parameters will be summarized.

Clinical laboratory test values, scheduled or unscheduled, will be considered PCS if they meet PCS criteria listed in [Table 2](#). The percentages will be calculated relative to the number of

subjects with available non-PCS baseline values with respect to the specific criterion and at least 1 post-baseline assessment. The numerator is the total number of subjects with a non-PCS baseline value with respect to the specific criterion and at least 1 post-baseline PCS value. A supportive listing will present all values for a parameter for subjects with at least one PCS value for that parameter.

Shift tables for shift from baseline to any post baseline visits during treatment period will be provided for selected chemistry, hematology, and urinalysis parameters with conventional reference limits (limits provided by the performing laboratories) for the Safety Population.

The following graphical displays will be presented by enrollment group and overall:

- Mean along with the corresponding standard error (SE) for selected chemistry and hematology laboratory parameters.
- Boxplots will be used to display summary statistics for the last assessment, maximum and minimum change from baseline values for selected chemistry and hematology laboratory parameters.

Pregnancy and drug test data will be listed.

Table 2: Criteria for Potentially Clinically Significant (PCS) Laboratory Parameters

Category	Parameter	Criteria
Hematology	Hematocrit	$\leq 32\%$ and 3 point decrease from baseline (Female) $\leq 37\%$ and 3 point decrease from baseline (Male)
	Hemoglobin	≤ 9.5 g/dL (Female) ≤ 11.5 g/dL (Male)
	Neutrophils	$< 1.5 \times 10^3/\mu\text{L}$

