	Platelets	$< 75.1 \times 10^3/\mu\text{L}$ $\geq 700 \times 10^3/\mu\text{L}$
	WBCs - total, differential (absolute)	$\leq 2.8 \times 10^3/\mu\text{L}$ $\geq 16 \times 10^3/\mu\text{L}$
	lymphocytes	$< 0.5 \times 10^9/\text{L}$
	Eosinophils	$> 1.0 \times 10^3 \text{ cells}/\mu\text{L}$
Chemistry	ALT	$\geq 3 \times \text{ULN}$
	Albumin	< 2.5 g/dL
	ALK-P	$\geq 3 \times \text{ULN}$
	AST	$\geq 3 \times \text{ULN}$
	Bicarbonate	< 15 mmol/L > 31 mmol/L
	BUN	> 30 mg/dL

Category	Parameter	Criteria
	Calcium	< 8.2 mg/dL > 12 mg/dL
	Chloride	\leq 90 mmol/L \geq 118 mmol/L
	Creatine Kinase	$> 3 \times$ ULN
	Creatinine	\geq 2 mg/dL
	Gamma Glutamyltransferase	$\geq 3 \times$ ULN
	Glucose	< 50 mg/dL > 200 mg/dL
	HDL Cholesterol	\leq 30 mg/dL
	Lactate Dehydrogenase	$> 3 \times$ ULN
	LDL Cholesterol	\geq 160 mg/dL
	Phosphate	< 2 mg/dL > 5 mg/dL
	Potassium	< 3 mmol/L > 5.5 mmol/L
	Prolactin	$> 1 \times$ ULN
	Sodium	< 130 mmol/L > 150 mmol/L
	Thyroid stimulating hormone (TSH)	$> 5.5 \mu\text{IU}/\text{mL}$
	Total Bilirubin	\geq 2 mg/dL
	Total Cholesterol	$> 300 \text{ mg/dL}$
	Triglycerides	$\geq 120 \text{ mg/dL}$ (Female) $\geq 160 \text{ mg/dL}$ (Male)
	Uric Acid	$> 9 \text{ mg/dL}$ $> 8 \text{ mg/dL}$ (Female) $> 10 \text{ mg/dL}$ (Male)
Urinalysis	Glucose	at least 2+
	Protein	at least 2+

For liver function tests, the number and percentage of subjects will be summarized by upper limit of normal (ULN) category as follows:

- ALT (alanine aminotransferase), AST (aspartate aminotransferase) and ALK-P (alkaline phosphatase) will be summarized by normal, $> 3 \times \text{ULN}$, $> 5 \times \text{ULN}$ and $> 10 \times \text{ULN}$.

Number of subjects who meet Hy's Law criteria (total Bilirubin $> 2 \times \text{ULN}$ and ALT or AST $> 3 \times \text{ULN}$) will be summarized and corresponding listing will be presented.

In addition, number of Subjects with Lymphopenia by Maximum NCI-CTCAE Toxicity Grade 1-4 will be summarized. A listing with all post-discontinuation lymphocyte counts from subjects who require additional lymphocyte count monitoring visits, as per the protocol, will also be provided.

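### Three descriptive SAP summaries need small corrections: urinalysis counts ignore baseline status, the liver-test table has no row for >1 to <=3 x ULN, and age 55 falls in two age classes

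*SAP*

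**What the plan says.** **Urinalysis (SAP 3.6.5).** The rule reads: "For urinalysis, the number and percentage of subjects with abnormalities at any post-baseline visit will be summarized". It gives no baseline condition and no denominator. For potentially clinically significant (PCS) laboratory values, the same section takes percentages relative to the number of "subjects with available non-PCS baseline values with respect to the specific criterion and at least 1 post-baseline assessment". It also plans shift tables from baseline, limited to the treatment period, for chemistry, hematology and urinalysis parameters that it calls selected but does not name. SAP Table 2 has two urinalysis PCS criteria: glucose and protein, each at 2+ or more.

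**Liver tests (SAP 3.6.5).** The lead-in is "For liver function tests, the number and percentage of subjects will be summarized by upper limit of normal (ULN) category as follows". The single item beneath it says "ALT (alanine aminotransferase), AST (aspartate aminotransferase) and ALK-P (alkaline phosphatase) will be summarized by normal", then above 3, above 5 and above 10 x ULN. It does not say which of a subject's values decides the row. Total bilirubin has a PCS criterion (>=2 mg/dL) and enters the Hy's Law count, but has no ULN rows.

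**Age (SAP 3.2).** The demographics list gives "age category (18-19, 20-29, 30-39, 40-49, 50-55" and then a last class of 55 and over. SAP 3.1.1.4 and 3.6.2 define the age subgroup for adverse events as <55 and >=55.

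SAP sections 6, 8 and 9 place dataset specifications, programming specifications and mock tables in separate documents.

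**The concern.** Long-term safety is the first objective, and these tables describe it without a control arm. The reader has only baseline to judge a laboratory finding against.

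A urinalysis percentage that takes in subjects already abnormal at entry cannot be read as newly occurring, yet it stands beside PCS percentages that can. The distinction has some weight here: Protocol 3.2.3.2 names the kidney as a target organ in toxicology, and SAP 3.6.4 lists renal injury as an event of special interest.

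In the liver table, mild elevations have no place, so the rows do not account for every subject. In the demographics table, a subject aged 55 belongs to two classes, so the classes can add to more than 100%.

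**Working it through.** The plan gives no figure to reproduce. The check applies each rule as written.

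**1. Urinalysis.** Let *b* be the share abnormal at baseline for a parameter, *r* the share of those abnormal again after baseline, and *e* the share newly abnormal among subjects normal at baseline. The documents give none of these, so all three are assumptions.

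- Share reported as written = b·r + (1 − b)·e
- Share reported with the count limited to subjects normal at baseline = e
- Difference = b·(r − e)

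With e = 10%:

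| b | r | b·r + (1 − b)·e | As written | Restricted |
|---|---|---|---|---|
| 5% | 50% | 0.025 + 0.095 | 12.0% | 10% |
| 5% | 100% | 0.050 + 0.095 | 14.5% | 10% |
| 10% | 50% | 0.050 + 0.090 | 14.0% | 10% |
| 10% | 100% | 0.100 + 0.090 | 19.0% | 10% |
| 20% | 50% | 0.100 + 0.080 | 18.0% | 10% |
| 20% | 100% | 0.200 + 0.080 | 28.0% | 10% |

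The excess is 2 to 18 percentage points over this range.

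Two planned outputs could separate old from new findings. The PCS counts are restricted by baseline but cover only glucose and protein at 2+ or more. Protocol Table 3 lists many other urine parameters, among them occult blood, ketones, urine albumin and urine beta-2-microglobulin. The shift tables cover unnamed parameters and the treatment period only, while the abnormality count runs over any post-baseline visit and so includes Visit 16, two weeks after the end-of-treatment visit.

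**2. Liver tests.** Each subject's highest value, in multiples of ULN, is set against the rows, with normal read as at most 1 x ULN.

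| Highest value | Rows met | PCS (>=3 x ULN) |
|---|---|---|
| 1.0 | normal | no |
| 1.01, 2, 2.99 | none | no |
| 3.0 | none | yes |
| 3.01, 5 | >3 | yes |
| 5.01, 10 | >3, >5 | yes |
| 10.01 | >3, >5, >10 | yes |

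The upper rows nest and each is correct. The gap is above 1 and up to 3 x ULN. That band can be occupied from the start: Protocol 6.2.2 sets the De Novo limit for ALT and AST at 2 x ULN or more, so a value between 1 and 2 x ULN does not exclude by that criterion. If 5% to 30% of about 1000 subjects peak in the band for a given test (assumption), 1000 × 0.05 to 1000 × 0.30 = 50 to 300 subjects are in no row.

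**3. Age.** Every whole-number age from 18 to 65 was checked against the six classes. Only 55 falls in more than one. If 1% to 3% of 1000 subjects are 55 (assumption), 10 to 30 are counted twice and the classes sum to 1010 to 1030. With 50-54 in place of 50-55, each age falls in exactly one class.

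**The case against.** A reader might infer that all three rules miscount subjects. The documents do not support that. Only the age classes count anyone twice. The liver rows are sound nested thresholds with a band left out. The urinalysis rule counts what it announces and does not call the result treatment-emergent.

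A reader might also size the urinalysis problem by letting a background rate *p* build up over the 14 post-baseline samples (Visits 3 to 16) as 1 − (1 − p)^14. That does not measure this defect. Under the independence the formula assumes, limiting the count to subjects normal at baseline gives the same result. What matters is the share abnormal at baseline who are abnormal again.

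Nor are mild liver rises lost from the report. SAP 3.6.5 provides by-visit chemistry summaries with change from baseline, boxplots of maximum change and shift tables for selected parameters, and full listings. A shift table against the laboratory limits would show normal-to-high moves if liver tests are among those selected, but it would not separate rises up to 3 x ULN from larger ones.

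Renal safety does not rest on the urinalysis count alone: creatinine, BUN, urine protein and urine glucose have PCS criteria, and TEAEs and SAEs are summarized by baseline GFR. Bilirubin is covered by its PCS criterion and the Hy's Law count, so ULN rows for it are a preference.

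Finally, the mock tables and programming specifications were not available and may already settle these points. That possibility stands, but the SAP text does not settle them.

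**Conclusion.** The point holds as a minor one about three descriptive tables; nothing here changes a study conclusion.

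- **Urinalysis** matters most. The percentage mixes pre-existing and new abnormalities, and the shift tables and PCS counts relieve this only in part. The illustration of 12% to 28% against 10% rests wholly on the assumed values of *b*, *r* and *e*. The excess shrinks to nothing if few subjects are abnormal at baseline.
- **Liver tests** have an omission: subjects peaking above ULN and up to 3 x ULN appear in no row. How many is unknown.
- **Age** is a true double count at 55, confined to the demographics table. The adverse event subgroups are not affected.

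**What to change.** 1. **Urinalysis (SAP 3.6.5):** for each parameter, count subjects normal at baseline who have at least one post-baseline sample, and show subjects abnormal at baseline separately. State the denominator.
2. **Liver tests (SAP 3.6.5):** add a row for >1 to <=3 x ULN, and state that subjects are classified by their maximum post-baseline value. The >3, >5 and >10 x ULN rows can stay cumulative. Rows for total bilirubin by ULN multiple are optional.
3. **Age (SAP 3.2):** change 50-55 to 50-54, which also agrees with the <55 / >=55 subgroup.

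The data are already collected. The cost is a few lines of SAP text and matching edits to table shells and programs, or a check that the separate shells already do this.

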#### 6.1.1. Rollover Subjects

In order to qualify for participation in this study, Rollover Subjects must meet all of the following criteria:

1. Is willing and able to provide informed consent.
2. Capable of understanding and complying with the protocol.
3. Agrees to use an acceptable method of contraception for the duration of the study and for 30 days after any study treatment administration or is surgically sterile or postmenopausal (see [Section 11.5](#)).
4. Completed the full treatment period of any eligible study of ALKS 8700 within 7 days of Visit 2.

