## **6.2. Exclusion Criteria**

### **6.2.1. Rollover Subjects**

Rollover Subjects will be excluded from participation in this trial if they meet any of the following criteria:

1. Have any finding(s) that in the view of the Investigator or Medical Monitor would compromise the safety of the subject, affect their ability to adhere to the protocol visit schedule, or to fulfill visit requirements or make the subject unsuitable for participation in the study (including overall clinical assessment).
2. Subject is pregnant or breastfeeding or plans to become pregnant or begin breastfeeding at any point during the study and for 30 days after any study treatment administration.
3. Is employed by Biogen, contract research organization (CRO), or study site (permanent, temporary contract worker, or designee responsible for the conduct of the study) or is immediate family of a Biogen, CRO, or study site employee. Immediate family is defined as a spouse, parent, sibling, or child, whether biological or legally adopted.

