3. DATA ANALYSES

3.1. Study Population

The study population, defined as all enrolled subjects who receive at least one dose of ALKS 8700, will be divided into three enrollment groups for summarizing safety and efficacy data:

1. De Novo Subjects
2. Rollover Subjects who were in ALKS8700 treatment group
3. Rollover Subjects who were in DMF treatment group

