3.6. Safety Analyses

3.6.1. General Considerations

All safety analyses will be carried out using the safety analysis set ([Section 3.1.1.1](#)) and will be summarized by enrollment group and overall unless specified otherwise.

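### The CTCAE lymphopenia table ignores the grade at entry, so its rollover and overall columns can mix lymphopenia brought from the antecedent study with lymphopenia that is new or worse in this one

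*SAP*

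**What the plan says.** The SAP's provision for graded lymphopenia is one clause at the end of section 3.6.5: the "number of Subjects with Lymphopenia by Maximum NCI-CTCAE Toxicity Grade 1-4 will be summarized". Safety results "will be summarized by enrollment group and overall unless specified otherwise" (SAP 3.6.1). The three enrollment groups in SAP 3.1 are De Novo Subjects, rollovers from ALKS 8700, and "Rollover Subjects who were in DMF treatment group".

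Elsewhere the SAP does refer to the starting point:

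- Potentially clinically significant (PCS) laboratory percentages are taken among "subjects with available non-PCS baseline values with respect to the specific criterion and at least 1 post-baseline assessment" (SAP 3.6.5). The lymphocyte criterion there is below 0.5 x 10^9/L.
- PCS vital signs use the same kind of denominator (SAP 3.6.6.1), and QTc percentages are limited to subjects with a baseline of at most 450 msec (SAP 3.6.6.2).
- An adverse event is treatment-emergent only if it starts or worsens on or after the first dose in this study (SAP 3.6.2).
- Shift tables cover "selected chemistry, hematology, and urinalysis parameters with conventional reference limits" (SAP 3.6.5). Lymphocytes are not named.

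Entry differs by route. For De Novo Subjects, the exclusion that begins "Has any of the following abnormal blood tests at screening" includes a lymphocyte count below 0.9 x 10^3/uL (Protocol 6.2.2). For rollovers the entry requirement is "Completed the full treatment period of any eligible study of ALKS 8700 within 7 days of Visit 2" (Protocol 6.1.1), and none of the three exclusions in Protocol 6.2.1 contains a laboratory threshold.

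**The concern.** A worst-grade count reads as the amount of lymphopenia seen on ALKS 8700 in this study. That reading needs the subjects to start without lymphopenia, or the count to be limited to worsening. De Novo Subjects largely meet the first condition through the screening limit. Rollovers need not, and there is no washout: Visit 2 falls at, or within 7 days of, the end-of-treatment visit of the antecedent study (Protocol 5.2). Because DMF and ALKS 8700 share the active metabolite MMF (Protocol 3.3), a low count at Visit 2 may well still be low at Day 15.

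Long-term safety is the first objective. The lymphocyte count drives withholding of treatment, permanent discontinuation and the follow-up of up to 6 months, so this table will be read closely. As planned, its columns do not start from the same point, and it cannot separate a subject who worsened in this study from one who arrived with the same low count.

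**Working it through.** There is no figure in the plan to reproduce: no formal sample size calculation, no lymphopenia rate, no rollover share and no entry prevalence. The check is of the text, followed by a labelled illustration.

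**1. Does the count refer to entry?** SAP 3.6.5 names no baseline grade or worsening requirement for it. It also does not say whether Visit 2 values, or values from the post-treatment lymphocyte monitoring visits, enter the maximum. No other section of either document supplies these.

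**2. Can two different histories look the same?** The protocol's normal limit is 0.91 x 10^3/uL and its follow-up threshold is 0.8 (Protocol 5.5, Table 2). Take two rollovers:

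- Subject A: 0.85 at Visit 2, lowest later value 0.55.
- Subject B: 0.55 at Visit 2, lowest later value 0.55.

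Both have a worst value of 0.55, so they share a maximum grade whatever the CTCAE cut-offs are (the documents do not give them). Neither is PCS, since 0.55 is not below 0.5. With Visit 2 as baseline and 0.91 as the laboratory's lower limit, both are low-to-low in a shift table. Yet A crossed 0.8 in this study and B did not change.

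**3. Which baseline do the other outputs use for rollovers?**

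| Source | Rollovers from ALKS 8700 | Rollovers from DMF |
|---|---|---|
| Protocol 12.3 | antecedent-study baseline | antecedent-study baseline |
| SAP 3.2 (demographics and baseline characteristics only) | carried over from the antecedent study | Visit 2 |
| SAP 3.6.5 (laboratory) | not stated | not stated |

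Under the Protocol 12.3 definition, a fall that occurred on DMF in the antecedent study would also appear as a post-baseline change in the percent-change, shift and PCS tables. Those tables are therefore not a dependable correction until the baseline is settled.

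**4. Illustration of size.** Only N = 1000 comes from the documents. Assumed: rollover share f of 50% to 90%; entry prevalence p of lymphopenia among rollovers of 5% to 30%; new onset i of 10% or 25% among those without it at entry; no carried-in cases among De Novo Subjects; and every carried-in case persisting to at least one counted sample.

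- Carried-in subjects: c = N x f x p
- New cases: (N - c) x i
- Overall percentage shown: [c + (N - c) x i] / N
- Excess over i: f x p x (1 - i)

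| f | p | c | Shown, i = 10% | Excess (points) | Shown, i = 25% | Excess (points) |
|---|---|---|---|---|---|---|
| 50% | 5% | 25 | (25 + 97.5)/1000 = 12.25% | 2.25 | (25 + 243.75)/1000 = 26.88% | 1.88 |
| 70% | 15% | 105 | (105 + 89.5)/1000 = 19.45% | 9.45 | (105 + 223.75)/1000 = 32.88% | 7.88 |
| 90% | 30% | 270 | (270 + 73)/1000 = 34.30% | 24.30 | (270 + 182.5)/1000 = 45.25% | 20.25 |

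Carried-in cases make up between 25/268.75 = 9% and 270/343 = 79% of the count. If some carried-in cases resolve before the first counted sample, the excess is smaller. The range shows that the effect could be trivial or large; it is not an estimate.

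**The case against.** The strongest reply is that this is one descriptive count among several lymphocyte outputs. The SAP also plans change from baseline and percent change in lymphocytes by visit, and boxplots of the minimum and maximum change and shift tables, each for selected parameters. It adds the PCS table and lymphopenia as an adverse event of special interest. Rollovers from DMF have their own labelled column, and no between-group test is planned. Dataset specifications, programming specifications and mock tables are separate documents (SAP 6, 8 and 9) and may define the window and denominator.

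Much of this stands and limits the point. A reader might infer that worsening on ALKS 8700 is invisible throughout the plan; the outputs just listed show that this goes too far. What they lack is a within-subject view by grade. By-visit summaries and boxplots describe groups, PCS covers only values below 0.5, and the shift tables use reference limits. A laboratory abnormality becomes an adverse event only if it meets serious-event criteria, needs corrective therapy or is judged clinically significant (Protocol 11.1.1).

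A reader might also infer that all carried-in lymphopenia is wrongly charged to ALKS 8700. In rollovers from ALKS 8700 it arose on the study drug. Removing those subjects from the main result could understate long-term risk, so a rate restricted to subjects free of lymphopenia at entry should not replace the full count.

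Nor do the documents establish that rollovers can enter at any grade, or that every rollover who is lymphopenic at entry is counted. The antecedent study's stopping rules are not shown, the investigator or Medical Monitor may exclude a rollover on safety grounds, and a count that recovers early may fall outside an undefined window.

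**Conclusion.** The point holds for the CTCAE table. As written, its rollover and overall columns can combine lymphopenia present at entry with lymphopenia that began or worsened in this study, while the De Novo column is largely protected by the screening limit. For rollovers from DMF, the carried-in part arose on another drug. For rollovers from ALKS 8700, the misassignment is of study and timing only.

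The conclusion rests on the text: a count with no entry reference, different entry limits by route, and no washout. It does not rest on the illustrated 2 to 24 points, which depend on assumed prevalence, rollover share, onset and persistence. The actual size cannot be known from the documents. The defect is confined to one table, with partial context elsewhere, but that context depends on a laboratory baseline that the documents leave unsettled for rollovers.

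**What to change.** In SAP 3.6.5, replace the sentence with wording to this effect:

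> The worst CTCAE lymphocyte grade after first dose in this study (window to be stated, including whether follow-up and lymphocyte monitoring visits count) will be cross-tabulated against the grade at the last value before first dose in this study, by enrollment group and overall. The number of subjects whose grade worsened will be reported. The maximum-grade count for all subjects will be shown alongside. For rollovers from ALKS 8700, the grade at the antecedent-study baseline will also be shown where available.

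The cross-tabulation should lead. Keeping the full count beside it ensures that drug-caused cases in rollovers from ALKS 8700 are not dropped, and the antecedent grade shows change over the whole period on the drug.

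State in the SAP which laboratory baseline applies to each rollover group, reconciling Protocol 12.3 with SAP 3.2, and carry that choice through the percent-change, shift and PCS tables.

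The cost is SAP wording and one extra table. The entry value is already available from Visit 2 or from the carried-forward end-of-treatment assessment; the antecedent-study baseline has to come from that study's data. If a worsening percentage is shown, its at-risk denominator will be smaller for rollovers and should be printed.
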